### 6.5 Indirect calorimetry

Calorimetry is the measurement of energy expenditure (EE). Direct calorimetry measures total heat loss from the body; indirect calorimetry measures total energy produced by the body. In this study, the metabolic rate measurements (VO2, VCO2 and EE) will be made using an open-system indirect calorimeter Deltatrac®(107). For the measurement, the subject's head is placed under a plastic transparent hood (canopy) connected to the analyzer. The collection of expiratory gases is performed in the resting, fasting state and during the OGTT (supine position). Energy expenditure, glucose, lipid and protein oxidation will be calculated as described (108).

### 6.6. Bioimpedance

Bioimpedance is done for the measurement of body fat content using electrical scale (Omron BF400). Bioimpedance is based on measuring electrical signals passing through the fat, lean mass and water in the body. The actual impedance or conductivity of various tissues in the body is known so by measuring current between two electrodes and applying this information to complex proven scientific formulas, body composition (i.e. body fat content) can be determined.

## 6.7. Timing of laboratory measurements

Screening laboratory tests include CBC (complete blood count: platelet count, red blood cell count, white blood cell count, haemoglobin, hematocrit, mean corpuscular volume, mean corpuscular haemoglobin, mean corpuscular haemoglobin concentration), urate and thyrotropin (TSH). In

addition a dexamethasone of 1 mg test is done. Laboratory tests in this study include basic tests and additional tests. Tests are done according to Table 1 and Table 2 below. Basic and additional laboratory test –packages are taken pre-operatively before VLCD and 6 months post-operatively

SCREENING TESTS	PREOPERATIVE TESTS*	POSTOPERATIVE TESTS				
Exclusion tests	Preoperative tests*	Post operative tests: 6 months				
Basic tests	Basic tests	Basic tests				
Additional tests	Additional tests	Additional tests				
D-25, B12, fE-folate	Calorimetry	Calorimetry				
Calorimetry	Bioimpedance	Bioimpedance				
Bioimpedance	PET samples PET samples					
*Subject has been accepted f	or the surgical treatment of obesity					
In addition, weight, BMI and measured using electrical sca	waist circumference are measured in eve le (Omron BF 400).	ery time point. Bioimpedance is				

Table 1: Laboratory tests and other measurements

Table 2: Laboratory test- kits

EXLUSION TESTS	BASIC TESTS							
PVK+T	INR(coagulation)	Oral glucose tolerance test with insulin, fatty acid and c-peptide measurements (OGTT, 75g glucose load, time points 0 and 120 minutes)	Blood radioactivity					
Thyrotropin (TSH)	Albumin	High sensitivity C-reactive protein (hs-CRP)	With  F-THFA: blood free fatty acids					
Dexamethasone test of 1mg (DXM)	Fasting plasma glucose (fd-gluk)	Non-cholesterol sterols (squalene, cholesterol, desmosterol, lathosterol, campesterol, sitosterol, cholesterol, avenastarol)						
Urate	Glucosylated haemoglobin-A- fraction c (GHbA1c)	Bile acids						
	Alanin aminotransferase (ALAT)	P-cytokines (IL-1β, IL-1βab)						
	Alkaline phosphatise (AFOS)	S-adiponectin						
	Glutamyl transferase (GT)	S-leptin						
	Total cholesterol	Serum fatty acid composition						
	HDL-cholesterol	Lipoprotein fractions						
	LDL-cholesterol Triglycerides	Size of LDL and HDL particles Gastro-intestinal peptides (CCK, bombesin, gastrin-releasing peptide, GIP, GLP1, peripheral PYY, pancreatic polypeptide, oxyntomodulin, ghrelin, obestatin)						
	Creatine	Lipodomics (not in 24 months)						
	Electrolytes(Na, K, Ca)	Proteomics (not in 24 months)						
	Phosphate (Pi)							
The samples of all stud samples will be collect		nd stored in a similar way. The order of analysis	is random. Spare serum					

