## **3. OBJECTIVES AND HYPOTHESES**

## 3.1. Objectives:

The objectives of this study are to measure effect of weight loss and the possible differences between sleeve gastrectomy and gastric bypass:

- 1. On whole-body and fasting free fatty acid metabolism in myocardium, skeletal muscle, liver, pancreas, intestine, bone, brain and subcutaneous and visceral fat.
- 2. On total body fat and abdominal fat distribution & abdominal fat volumes
- 3. On liver fat content
- 4. On glycemic control and on biochemical markers (leptin, ghrelin, adiponectin, HDL, LDL, triglycerides, cholesterol, calcium, B12-vitamin, cytokines, bile acids and high sensitivity C-reactive protein).
- 5. On brain white and gray matter volumes and distribution
- 6. On brain activation response to food stimuli before and after surgery
- 7. On the two specific neurotransmitter systems, dopamine and opioid
- 8. On correlation between brain activation to food stimuli and hormonal changes especially of the gastrointestinal peptides (e.g. ghrelin)
- 9. On correlation between the subjective feelings of hunger and brain activation
- **10.** On markers of bone metabolism (Vitamin D, PTH, S-Ctx, bsAP, PINP and osteocalcin) and bone mineral density
- 11. On quantitative and metabolic changes in the bone marrow fat

We also aim:

- **12.** To take DNA samples for further investigation on genetic markers related to cardiovascular diseases, type 2 diabetes and obesity risk factors as a part of CMGene-study
- 13. To investigate the effect of morbid obesity on the histology and thus take biopsies
  - a. During endoscopy from gastric mucus, duodenum, antrum and corpus
    - b. During surgery from liver, abdominal subcutaneous and visceral fat
- **11.** To investigate the effect of morbid obesity and the surgery-induced weight loss on the histology of abdominal subcutaneous adipose tissue by taking a biopsy from abdominal adipose tissue
- 12. To measure the effects of bariatric surgery on gene and protein expression in these tissue biopsies
- 13. To compare the general risk factors between sleeve gastrectomy (SG) and gastric bypass
- 14. To obtain information about the hormonal benefits and long-term results of SG
- 15. To investigate the effects of bariatric surgery on intestinal perfusion and metabolism.
- **16.** To investigate the effects of bariatric surgery on the rate of bone turnover and bone quality using paired bone biopsies
- **17.** The rate of bone turnover (bone biopsy),

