## 5. PATIENT/SUBJECT SELECTION

## 5.1 Source population

The study consists totally of 60 study subjects. Of these 40 are morbidly obese adults (male of female,  $BMI \ge 40 \text{ kg/m}^2$  or if there is additional risk factor  $BMI \ge 35 \text{ kg/m}^2$ ) and they will be recruited from patients undergoing the surgical procedure as a part of normal treatment mode. The morbidly obese patients are randomized either for laparoscopic sleeve gastrectomy (n=20) or Roux-en-Y gastric bypass (n=20). For a control group 20 lean, healthy, age and sex matched subjects will

be recruited. The control subjects will be recruited according to personal contacts, electrical and traditional bulletin boards, and newspaper advertisements.

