## 12. STATISTICS

## 12.1. Sample size

The number of subjects to be recruited is based on power analysis. Joint analysis based on all the variables of interest suggest that sample size of 20 plus 20 patients and 20 controls is sufficient for detecting statistically significant differences at alpha level of 0.05.

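### The random order of laboratory analysis does not keep a patient's pre- and post-operative samples in one run, so batched assays over several runs lose precision on within-patient change

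*Protocol*

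**What the plan says.** Protocol section 6.7 has the basic and additional laboratory packages "taken pre-operatively before VLCD and 6 months post-operatively". The footnote to Table 2, part of which is damaged in the text at hand, is legible on the order of assay: samples are "stored in a similar way. The order of analysis" "is random. Spare serum" (the last two words begin the next sentence). It does not mention runs, plates or batches, or whether a patient's two samples stay together.

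The targets are changes. Section 3.1 sets out to "measure effect of weight loss and the possible differences between sleeve gastrectomy and gastric bypass". Its objective 4 covers the biochemical markers, and objective 8 the correlation of hormonal changes with brain activation. Section 2.2 aims to compare the change in hormone secretion between the two operations. Section 3.2.3 predicts that changes in activation go with changes in gastrointestinal hormones.

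Section 12.1 holds that a "sample size of 20 plus 20 patients and 20 controls is sufficient" "at alpha level of 0.05". It gives no effect size, SD or power.

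**The concern.** When the outcome is a change within a patient, an error shared by both of that patient's samples cancels. A run's calibration or reagent lot produces such an error, but only if both samples are in that run. The footnote randomises the order and says nothing about keeping pairs together. Followed as written, with an assay that needs several runs, it will split some pairs, and the difference between two runs is then counted as part of those patients' change.

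Three analyses would lose precision: the mean change in all 40 patients, the comparison of change between arms of 20, and the correlations of hormone change with change in brain activation, which assay noise pulls towards zero. The layout is fixed once the assays are run. Adjustment for run in the analysis could recover part of the loss, if the run is recorded, but pairing avoids the loss altogether.

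**Working it through.** **The plan's own figure.** The sample size cannot be reproduced, because section 12.1 gives no difference, SD or power. Read backwards, 20 per arm at two-sided 0.05 and an assumed 80% power detects a standardised difference of (1.960 + 0.842) × √(2/20) = 0.886.

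**Number of samples.** 40 patients × 2 + 20 controls once = 100 per assay. The budget in section 16 also lists 100 lipidomics analyses. It places them all in 2013, after scans budgeted for 2011 and 2012, so at least that part of the panel appears to be assayed as a batch after collection.

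**Chance that a pair is split.** With N = 100 samples in random order and runs of size s:

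P(split) = 1 − Σ s(s − 1) / [N(N − 1)]

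For runs of 40, 40 and 20: 1 − (1560 + 1560 + 380)/9900 = 1 − 3500/9900 = 0.65.

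**Variance of a change score.** Let B be the biological SD of change, w the within-run CV and b the between-run CV:

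Var = B² + 2w² + 2 × P(split) × b²

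This is an average over random orders. Run errors shared by different patients cancel on average, so the difference between arms is inflated by the same ratio.

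Assumed, because the protocol gives none of them: B = 25%, w = 5%, b = 10%.

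- Paired: 625 + 50 = 675, SD 26.0%.
- Random order, runs of 40: 625 + 50 + 2 × 0.65 × 100 = 805, SD 28.4%. Ratio 805/675 = 1.19.
- Every pair split: 625 + 50 + 200 = 875, SD 29.6%. Ratio 875/675 = 1.30.

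**Power.** For a comparison between arms with 80% power when paired, power = Φ(2.802/√ratio − 1.960). The number per arm that restores 80% is 20 × ratio, rounded up.

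| Run sizes | P(split) | Variance ratio | Power | Per arm to restore 80% |
|---|---|---|---|---|
| 100 | 0 | 1.00 | 0.80 | 20 |
| 80, 20 | 0.32 | 1.10 | 0.76 | 22 |
| 50, 50 | 0.51 | 1.15 | 0.74 | 23 |
| 40, 40, 20 | 0.65 | 1.19 | 0.73 | 24 |
| five of 20 | 0.81 | 1.24 | 0.71 | 25 |
| every pair split (bound) | 1 | 1.30 | 0.69 | 26 |

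**Detectable difference between arms** (0.886 × SD): 0.886 × 26.0 = 23.0% paired, and 0.886 × 28.4 = 25.1% with runs of 40.

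**Correlations.** A true correlation of 0.50 with hormone change would be observed, on account of assay error alone, as 0.50 × √(625/675) = 0.48 when paired and 0.50 × √(625/805) = 0.44 with runs of 40.

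**Range.** A second grid took the biological CV per sample as 10% to 30%, within-run/between-run CVs of 5/5, 5/10 and 8/15, and P(split) of 0.5 to 0.8. The ratio runs from 1.01 to 2.10, and 80% power falls to between 0.795 and 0.49. The top of the range needs a small biological CV together with a poor assay.

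**The case against.** The best defence is that random order is a sound rule. It keeps assay drift from lining up with time point or arm, so comparisons stay unbiased. The footnote says random and no more, which would also fit pairs randomised together or order randomised within runs, and a laboratory manual may hold the run layout. The main hypotheses in section 3.2 concern mostly imaging and bone, with the hormones as correlates.

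Much of this stands. A reader might infer that the order is fully random by design, that every change score is affected, or that the results are biased. The documents support none of these:

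- No text calls the order unrestricted. It simply states no restriction.
- Pairs that fall in the same run, and assays done in one run, carry no between-run error in the change.
- Imaging, calorimetry and weight changes are unaffected. So are tests run at each visit, where pairing is impossible anyway. Table 2 includes routine tests such as INR, glucose and electrolytes, and the protocol does not say that these are stored and batched.
- The ratio of 1.30 needs every pair to be split, which random order with runs of 20 or more would not be expected to produce.

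The defence does not show that the stated rule protects the pairs. The protocol chose to fix the order of assay, and a laboratory that follows the sentence as it stands will split pairs whenever there are several runs. Pairing within runs keeps the protection against drift, because patients of both arms are still spread over the runs and order within a run is still random.

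**Conclusion.** The point holds for stored samples assayed in batches over more than one run. There the stated order lets between-run error into the change scores of the patients whose samples are split, and so lowers precision for the hormone and biomarker changes in objectives 4 and 8. It does not make those comparisons invalid.

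The size is uncertain, because the protocol gives no assay CVs, run sizes or number of runs. Under the illustrative CVs and runs of 40, the loss equals about 4 patients per arm (24 instead of 20). It is nil if an assay fits in one run. With arms of 20 there is little precision to spare, and the loss can be avoided almost without cost, so the sentence is worth changing. The missing assumptions in section 12.1 are a separate matter.

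**What to change.** Replace the sentence on order in the Table 2 footnote with:

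*For batch-analysed stored samples, both samples of a patient are analysed in the same run; patients of both arms and controls are spread over the runs; the order within a run is random.*

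The cost is a different plate layout, with no extra samples or assays. Pre-operative samples must be held until the 6-month sample is in, which the budget's timing already implies for lipidomics.

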### 6.8. Biopsies, proteomics and DNA samples

#### Human tissue biopsies

During endoscopy routine biopsies are taken from duodenum, antrum and corpus. Biopsies from liver, subcutaneous and visceral fat will be taken during bariatric surgery and subcutaneous fat biopsies 6 months postoperatively under local anaesthesia using 1 % lidocaine without adrenaline. Tissue samples will be cut into samller pieces and immediately stored in formalin or frozen in liquid nitrogen and stored in -70°C.

Bone biopsies will give very important insight into the bone metabolism in morbid obesity as well as after bariatric surgery. Dynamic and static histomorphometric analysis is the golden standard to analyse changes in bone turnover. Transiliacal bone biopsies are taken from the anterior iliac crest in conjunction of the surgery as well as 6 months after the surgery (from the opposite side). The biopsies will be harvested under local anaesthesia in the operation theatre as described in Tamminen et al. 2007. Samples will be fixed in ethanol and analyzed in the bone biopsy unit of the Kuopio University Hospital. Separate written informed consent is done for bone biopsy sampling.

#### RNA isolation and expression analysis

Total RNA will be isolated from human tissues with Trizol (Invitrogen, Carlsbad, CA), from HepG2 and C2C12 using RNeasy with DNase 1 treatment (Qiagen, Valencia, CA). cDNA will be synthesized using random hexamers (Advantage, Clontech, Mountain View, CA), for subsequent real-time qPCR (ABI Prism 7000 or 7700 Sequence Detection System, Applied Biosystems, Inc., Foster City, CA). PCR products will be detected using SYBR Green or Taqman pre-designed Assays-on-Demand.

#### Protein isolation and expression analysis

Frozen tissue samples will be lysed in buffer containing protease inhibitor cocktail (Sigma), sodium fluoride (100 mM), sodium orthovanadate (2mM) and 1 % Triton X-100. Protein concentrations will be determined using a BCA kit (Pierce Biotechnology, Rockford, IL) and proteins will be separated by SDS-PAGE for subsequent Western blotting.

#### DNA samples

DNA samples are collected and used according to another study protocol: CMGene. Separate written informed consent is done for DNA sampling. Results from the DNA studies are not given to the subjects.

## 7. SAFETY

During PET studies: Heart rate and blood pressure will be monitored during the studies. Chemical purity of [C]raclopride, [C]carfentanil and [F]FTHA are measured before administration. Stable isotopes are commercial sterile products.

## 8. ADVERSE EVENTS

### 8.1. Reporting of Adverse events (AE's)

All adverse events will be registered, and when necessary, the ethical committee and the National Agency for Medicine will be notified. All adverse events will be fully documented and followed in order to determine the final outcome (until the event has subsided or the condition as stabilised).

## 8.2. Expedited Reporting

According to Finnish national regulation, serious adverse event\* will be reported to suitable authorities within 3 days whereas unexpected or unusually severe adverse experience\*\* will be reported within ten days.

\*A serious adverse event is any event that is fatal, life-threatening, disabling, incapacitating, results in hospitalisation, or prolongs hospitalisation.

\*\*A severe adverse experience is any event that prevents normal everyday activity.

## 8.3. Emergencies

Emergencies may occur during the experiments. A medical doctor will be present during all the measurements in the study. Vital functions will be monitored, and materials and drugs needed for first aid/resuscitation are readily available.

## 9. ETHICS

## 9.1. Ethical considerations

The studies will be performed using standard procedures that have been in clinical or research routine use for years in the Turku PET Centre. This study will be conducted according to Good Clinical Practice and the Declaration of Helsinki. Written informed consent for the study will be obtained from all subjects before the beginning of the study. Subjects will be informed of their right to withdraw from the study at any time. At least one medical doctor will be available at all times during the study. All necessary investigator contact information will be provided along with a description of the study. The radiation dose fof patients will be around 22.5 mSv which is approximately 4.4 times the natural background radiation in Finland for one years. Although there is no exact knowledge about the risk for developing cancer after this dose of radiation, the risk of fatal cancer is estimated to correspond to the risk for dying when driving 22500 kilometres in a car or smoking 225 cigarettes (109). As the control group is studied only once the radiotion dose will be around 11.25 mSv.

## 9.2. Ethical Review

Study protocol, patient information, and informed consent form will be submitted to the Ethical Committee of the Hospital District of the South-Western Finland and studies will not start before getting ethical permission. The ERC/IRB will be informed by the Investigator of all subsequent protocol amendments and of serious or unexpected adverse experiences occurring during the study, which are likely to affect the safety of the subjects or the conduct of the study.

## 9.3. Subject information and informed consent

Information about the study procedures and design will be given in both oral and written form to the study subjects. All necessary investigator contact information will be provided along with a description of the study. Written informed consent for the study will be obtained from all subjects before the beginning of the study. The principles of informed consent in the current edition of the Declaration of Helsinki will be implemented. Subjects will be informed of their right to withdraw from the study at any time.

## **10. DATA COLLECTION AND MANAGEMENT**

## 10.1. Case Report Forms

One set of case report forms will be filled during the initial clinical examination in order to collect subjects' personal information and their medical status and history relevant to the aims and exclusion criteria of this study.

## 10.2. Electronic data collection

Data from the case report forms, clinical observations (such as adverse effects or changes in medical status) as well as results from the study (biological and PET results) will be gathered in electrical form.

## 10.3. Data management

All data collected is strictly confidential. It will be archived on paper or electronically at least for fifteen years

## 11. DATA ANALYSIS

## 11.1. Analysis of PET-data

For calculation of skeletal muscle, myocardial, liver, pancreas, and adipose tissue FFA uptake the three compartment model (110) and graphical analysis (75) are employed. Plasma and tissue time-activity curves are analysed graphically to quantify the fractional rate of the tracer transport, KI (73).

## 11.2. Analysis of MRI data

The software SliceOmatic is used to measure the adipose tissue mass before and after the surgery. Then data will be extracted to SPSS for further analysis.

## 12. STATISTICS

## 12.1. Sample size

The number of subjects to be recruited is based on power analysis. Joint analysis based on all the variables of interest suggest that sample size of 20 plus 20 patients and 20 controls is sufficient for detecting statistically significant differences at alpha level of 0.05.

## 12.2. Statistical plan

Appropriate statistical analyses will be performed corresponding to current standards.

## 12.3. Possible interim analyses and stopping rules

No interim analysis is intended.

## **13. QUALITY ASSURANCE**

## 13.1. Information of study personnel and training

All the involved personnel at the participating centres will be informed about the aims and the practical issues of the study. The measurements are routinely performed at the Turku PET Centre and have been applied for years.

## 13.2. Protocol amendments

According to Finnish regulations, protocol amendments can be made if all investigators agree. They are presented in a written form and dated. They include the original chapter of the study protocol and the amended chapter with and explanation of this change. All important protocol amendments will be submitted for review to the ethical committee and the National Agency for Medicine.

## 14. STUDY SCHEDULE

The clinical part of the project will be spread for three years (01.01.2011 to 31.12.2013). Analysis and reporting of the data will be started as soon as possible.

## **15. CRITERIA FOR PREMATURE STUDY TERMINATION**

No interim analysis is intended.

## 16. FINANCING

The study will be financed with project grants of [name] (EFSD 300 000€), [name] and [name] (Sigrid Juselius 140 000€). Other research grants will be applied for study financing from the CoE funding from Academy of Finland (the study and the researchers are part of "Finnish Centre of Excellence in Molecular Imaging in Cardiovascular and Metabolic Research", Ministry of Education), and from several foundations.

The study has neither a straight nor indirect financing from the industry. The financing of the study is governed through the TYKS and University of Turku.

Study budget	Unit	Year 2011Year 2012Year 2013		2013	Year	2014	Total n of studies	TOTAL (€)			
PET (18F)FTHA (2x40[contact]	16400		0		0	100	32 800
PET (11C)RAK (2x40[contact]	50	15 100		0		0	100	30 200
PET (11C)CAR (2x40[contact]	17400		0		0	100	34 800
MRI+FMRI+MR S	400	50	20000	50	20000		0		0	100	40 000
FMRI controls 6 mo	246	10	2460	10	2460		0		0	20	4 920
Echocardiograph y(all subjects pre and post)	200	60	12000	60	12000					120	24 000

OGTT	60	50	3000	50	3000		0		0	100	6 000
Travelling cost of study subjects	30	320	9600	320	9600		0		0	640	19 200
Lipidiomics	300		0		0	10 0	30000		0	100	30 000
Analysis of tissue biopsies	150		0		0	80	12000		0	80	12 000
Travelling cost of researchers	2000		0		0	7	14000	8	16000	15	30 000
Publication costs	700		0		0	5	3500	5	3500	10	7 000
Salary of one research nurse	2465	12	29580	12	29580		0		0	24	59 160
Salary of 3 PhD student	2600	36	93600	36	93600	36	93600	36	93600	144	374 400
Salary of one senior researcher	6200	12	74400	12	74400	12	74400	12	74400	48	297 600
			293540		293540		227500		187500		1 002 080

The study subject fee will be paid only for the control subjects. The study subject's fee will be totally 300€ If the patient consents to the bone biopsies 100€ will be paid. Travelling expenses will be paid according to prices for public transportation

